- Précis:** A total of 72 subjects 18 years or older will be recruited and examined for this 1-8 visit, up to 56 days research study. Assuming a 10% dropout in both groups, healthy individuals (n=36) and individuals with severe periodontal disease (n=36) will be evaluated at 2 main timepoints: baseline and 21-days of biofilm overgrowth (visit 5). Visit 1 includes enrollment and alginate impressions for a stent fabrication; visit 2 includes plaque collection, gingival biopsy and delivery of the stent; visits 3 and 4 are designed for monitoring disease; visit 5 includes collection of gingival biopsies and dental plaque and discontinuation of the stent usage. Analysis will include characterization of the expression of IFI16 and AIM2 (mRNA and protein) in gingival tissues in chronic and acute inflammation, and further characterization of the main cells expressing these proteins. Clinical outcomes will include measurements of periodontal disease, including as CAL, PD, BOP, GI, and PI. Plaque samples will be evaluated for the presence of periodontal pathogens. Visits 6-8 will be completed in 30 days from visit 5 and are for prophylaxis and SRP based on individual need.
- Objectives:** Primary: To characterize the expression of IFI16 and AIM2 in gingival tissues in an inflammatory response using the stent-induced biofilm overgrowth model.
- Population:** Adult subjects will be recruited from the patients, students and staff at the University of North Carolina, as well as the general population in or near Chapel Hill NC. Inclusion criteria for subjects includes a diagnosis of a healthy and severe periodontal disease according to periodontal and tooth profile classification system (1). Individuals will be classified based on an algorithm that relies on the periodontal clinical parameters, presence of teeth and crowns. Subject exclusion criteria include a history of autoimmune diseases, diabetes, immunocompromised subjects, neurologic or psychiatric disorders, systemic infections, use of chronic medications

known to affect the periodontium, smokers, and untreated dental conditions.

[figure not shown]
Number of Sites: General and Oral Health Center, UNC School of Dentistry

Study Duration: 60 Months

Subject Participation Duration: Up to 56 Days

Estimated Time to Complete Enrollment: 36 Months

Figure 1: Schematic of Study Design:

2 INTRODUCTION: BACKGROUND INFORMATION AND SCIENTIFIC RATIONALE

2.1 Background Information

The host response is recognized as the major contributor to periodontal tissue damage by supporting a non-resolving inflammation and sustaining dysbiosis (2). Our group has recently shown that interferon, gamma-inducible protein 16 (IFI16) and absent in melanoma (AIM2) are potentially involved in the pathogenesis of periodontal disease (3, 4). IFI16 and AIM2 are intracellular recognition sensors that modulate inflammatory responses against several microorganisms. Our data shows that IFI16 and AIM2 are expressed in multiple cells of human gingival tissues (4). In murine experimental periodontitis, these proteins significantly increase in comparison to mice with healthy gingival tissues. This suggests that pathways of IFI16/AIM2 could be interesting for a future therapeutic development to treat periodontal diseases. However, the expression of IFI16 and AIM2 has not been fully characterized in human gingival tissues. Thus, we propose to characterize the gingival tissue expression of IFI16/AIM2 in distinct periodontal conditions represented in healthy and periodontal diseased subjects to elicit chronic and acute responses using the stent-induced biofilm overgrowth model. This master protocol document describes the procedures for such an experiment that represents the clinical portion and the first aim of a larger three aim study of IFI16.

2.2 Rationale

Periodontal disease is a biofilm-induced inflammatory disease that affects the integrity of the tissues that surround and support the teeth (5). Severe periodontitis is the 6th most prevalent disease worldwide, with an overall prevalence of 11.2% and 734 million people affected. In the U.S. Periodontal disease affects 47% of the adult population (6, 7). Periodontitis is a major cause of tooth loss in adults, having subsequent impact on the person's masticatory dysfunction, quality of life and self-esteem (8). The global cost of lost productivity from severe periodontitis alone has been estimated to be 54 billion USD/year. Such burden of periodontitis will continue to increase with the growing ageing population with increased tooth retention globally (8-10). While treatment of periodontal disease is successful in the majority of cases, up to 30% of patients with moderate chronic periodontitis respond poorly to treatment (i.e. refractory periodontitis) (11, 12). Periodontal disease is a multifactorial disease that has microorganisms and a susceptible host as key players. The tooth-associated biofilm is required but not sufficient to induce periodontitis because it is the host inflammatory response to this microbial challenge that ultimately can cause destruction of the periodontium (13). The host response is now recognized as the major contributor to periodontal tissue damage by supporting a non-resolving inflammation and sustaining dysbiosis (2). Both innate and acquired immune responses are shown to be important for disease initiation and progression of periodontal disease (14). A recent consensus by the European Workshop on Periodontology recognizes that all current biological approaches to improve periodontal treatment have been focusing on direct microbial managements (antibiotic treatments) instead of approaches that will assist host response modulation (15). Concerns about the ever-increasing development of antimicrobial resistance

additionally supports methods for modulating the host response instead of drugs targeting a broad spectrum of microorganisms.

The innate immune function depends on recognition of pathogen-associated molecular patterns (PAMPS) derived from invading pathogens by germline-encoded pattern-recognition receptors (PRRs). Activation of PRRs triggers downstream, signaling cascades and leads to production of pro-inflammatory cytokines and chemokines (16). The balance between pro- and anti-inflammatory mediators determines the severity and extent of tissue destruction in the periodontium (17, 18). In order to re-establish the balance between mediators, anti-inflammatory pharmacologic agents [non-steroidal anti-inflammatory drugs (NSAIDs)] have been used to prevent and slow the progression of experimental and human periodontitis (15, 18, 19). While this host-modulation approach has shown to be successful, the side effects of NSAIDs have made the usage impossible for the routine treatment of periodontitis. Therefore, further understanding of the host response is a mean for future therapeutic development.

Inflammasomes are multimeric protein complexes that assemble in the cytosol after sensing PAMPs and danger-associated molecular patterns (DAMPs). Several inflammasome sensor molecules can trigger the formation of inflammasomes, including the nucleotide-binding domain, leucine-rich repeat containing proteins (NLRs, the largest family of inflammasomes), absent in melanoma 2 (AIM2)-like receptors and interferon gamma-inducible protein 16 (IFI16) (20). Inflammasome names denote from the protein forming the scaffold. While there are differences between inflammasomes dependent upon stimuli, classic inflammasomes serve as a scaffold to recruit inactive caspase-1. Oligomerization of pro-caspase-1 proteins induces their auto-cleavage into active caspase-1, which cleaves precursor cytokines into active IL-1 β and IL-18 (21). Inflammasomes are shown to play either causative or contributing roles in the initiation of a variety of auto-inflammatory and autoimmune diseases, including neurodegenerative diseases (multiple sclerosis, Alzheimer's disease and Parkinson's disease), and metabolic disorders (atherosclerosis, type 2 diabetes and obesity). Expression of several inflammasome components are altered in cells and tissues from diseased individuals (22). Recent in vitro and in vivo studies have pointed towards promising therapeutics that target inflammasome activity in inflammatory diseases, including inhibition of the NLRP3-inflammasome for the reduction of atherosclerosis lesions (22, 23).

AIM2 is the first member of the PYHIN protein family to be linked to the inflammasome (24). AIM2 is a cytosolic protein that is a well-characterized sensor of viruses and bacteria (25-27). Expression of AIM2 is increased in inflammatory conditions, including psoriasis, inflammatory bowel disease, atopic dermatitis and periodontitis, supporting a role of this protein in inflammatory diseases (4, 28-32). In vitro, Porphyromonas gingivalis (Pg) pro-inflammatory IL-1 β response is supported by AIM2-inflammasome activation (33). Therefore, AIM2-inflammasome may be important in driving the periodontal host response. The role of AIM2-inflammasome in the host response to other important periodontal pathogens and in experimental periodontitis has never been explored. While AIM2 is shown to be increased in chronic periodontitis (30, 31), the effect of this protein in inflammatory bone loss is unknown.

Recent studies from our group identified IFI16 as a potential protein important for periodontal disease pathogenesis (3) and recently published manuscript by the

applicant. Our study is the first to demonstrate expression of IFI16 in periodontal tissues (4). Expression of IFI16 is observed in multiple cells of the periodontal tissues, including epithelial cells, endothelial cells, fibroblasts and leukocytes.

IFI16 (mouse ortholog ifi204) is a multifunctional protein that has been well characterized as a pathogen sensor that leads to inflammasome activation and production of type I interferon and a pro-inflammatory response (25, 34, 35). IFI16 is also reported to be increased in inflammatory conditions, including psoriatic epidermis, inflammatory bowel disease (32, 36). Like other inflammasome proteins, the majority of studies support IFI16 as a pro-inflammatory molecule. However, IFI16 has also demonstrated an anti-inflammatory action *in vitro* by directly binding to AIM2 and suppressing activation of caspase-1 and further host response (37, 38) (Figure 2). **This suggests that, dependent on the type of stimuli and disease, IFI16 can have an anti-inflammatory function by dampening the AIM2-mediated inflammatory response.** However, these *in vitro* studies did not evaluate IFI16 as a modulator of inflammation upon bacterial infection. In addition, currently no *in vivo* study has evaluated IFI16 as a modulator of inflammation via AIM2 inflammasome. We continued our studies by inducing experimental periodontitis in *Ifi204^{-/-}* animals. Analysis of periodontal tissues shows that ***Ifi204^{-/-}* mice have a significant increase in the extent of alveolar bone loss** in experimental periodontitis ($p \leq 0.05$). Mean alveolar bone loss is 28.8% for WT and 47.74% for *Ifi204ko* mice in a 10-day period of ligature, representing **1.6-fold increase in the amount of bone loss.** Together, the data suggests that IFI16 acts as an anti-inflammatory protein by altering the expression of cytokine/chemokine responses. Better characterization of the cellular and molecular biology of inflammasomes will help identify important potential therapeutic targets for the treatment and prevention of periodontal diseases (39). The importance of IL-1 β and IL-18, in periodontal disease pathogenesis is shown in several clinical studies (40-45). Currently, therapies targeting IFI16 and AIM2 have not been developed. Studying these proteins individually and collectively, along with upstream and downstream events, will yield to new approaches to potentially treat periodontal disease severity and progression. This project will form the basis of a future project involving inflammasomes and alternative therapeutic approaches.

2.3 Potential Risks and Benefits

All research involves risks. This may include physical, psychological, social, legal and economic risks. There may be uncommon or previously unknown risks that might occur. Risks for this study are similar to those associated with other related dental procedures. Every participant will be encouraged to report any problems and/or health changes while enrolled in this research study. Participants will be given any new information gained during the course of the study that might affect their willingness to continue participation.

In spite of safety measures, a participant might develop a reaction or injury from being in this study. If such problems occur, the researchers will help get medical care for the

participant, but any costs for the medical care will be billed to the participant. The principal investigator or The University of North Carolina at Chapel Hill has not set aside funds to pay for any such reactions or injuries, or for the related medical care.

2.3.1 Potential Risks

Subjects may experience short-term discomfort and bleeding of the gums from periodontal probing as a result of the periodontal clinical examinations. This exam is not different from what would normally be performed in a dental or periodontal office to evaluate the condition of the periodontal tissues and extent of disease. No dental radiographs will be taken.

Subjects may experience short-term gingival inflammation, halitosis or bad mouth taste, dental plaque accumulation, and bleeding of the gums from refraining from all oral hygiene procedures (i.e., tooth brushing, flossing or use of interdental aids and/or mouthwashes) in the two selected sextants (up to 6 teeth in each arch) for 21 days. Subjects may continue plaque control procedures for the remaining four sextants using fluoride dentifrice and toothbrush. At the completion of the study, adult prophylaxis (for orally healthy individuals) or Scaling and Root Planing (SRP) (for individuals with periodontal disease) will be completed to restore gingival health eliminating gingival bleeding, dental plaque accumulation, and halitosis. Subjects will be monitored for safety every week and after the induction of experimental biofilm overgrowth through 21 days. Any site undergoing clinical attachment loss of >2mm from the baseline measurement will be deemed as “progressing” and participant will be exited from the study and given scaling and root planing treatment as a rescue therapy at the same day of the visit.

Subjects may experience mild to moderate discomfort, and bleeding during the scaling and planing procedure or adult prophylaxis. Transient bacteremia can occur after dental prophylaxis and SRP. Standard of care practices will be utilized for all scaling and root planing, adult prophylaxis and dental exams performed. In order to minimize discomfort, subjects will receive local anesthesia prior to scaling and root planing procedures. Although not required, subjects may receive topical anesthesia prior to and during the adult prophylaxis.

Subjects may experience moderate discomfort following treatment procedures, which will be performed under local anesthesia. Topical anesthesia is used initially to minimize the discomfort associated with local anesthesia injections. Local anesthesia may cause swelling, drooling, dizziness, tachycardia or muscle pain that should be temporary. There may be post-operative tenderness, sensitivity to hot or cold, slight bleeding or oozing, or development of a transient or permanent temporomandibular joint disorder. Some gingival recession or loss of papillae height may occur. Subjects receiving scaling and root planing procedures will be encouraged to use over the counter analgesics, according to the subject’s medication tolerance, to control any post-operative pain.

Subjects may experience moderate discomfort following treatment or biopsy procedures, which will be performed under local anesthesia. Topical anesthesia is used initially to minimize the discomfort associated with local anesthesia injections. Local

anesthesia may cause swelling, drooling or muscle pain that should be temporary. There may be post-operative tenderness, sensitivity to hot or cold, slight bleeding or oozing, or development of a transient or permanent temporomandibular joint (TMJ) disorder. Some gingival recession or loss of papillae height may occur. Subjects receiving biopsy and/or scaling and root planing procedures will be encouraged to use over the counter analgesics, according to the subject's medication tolerance, to control any post-operative pain.

In this study, the following events will not be considered reportable AEs:

- Short-term discomfort, bleeding or oozing of the gums, tooth sensitivity, cheek biting, gingival soreness, mild gingival inflammation, mild gingival bleeding, mild tooth mobility, mild gingival abrasion or irritation, as a result of the periodontal assessments, local anesthesia or periodontal treatment.
- Gingival recession or loss of gingival papillae
- Short term jaw soreness resulting from periodontal assessments or periodontal treatment

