5.2 Subject Exclusion Criteria

An individual who meets any of the following criteria will be excluded from participation in this study:

- If the sextants identified for the analysis has implants
- All individuals who meet criteria for anti-infective prophylaxis prior to dental procedures should be excluded from this study.
- Chronic disease with oral manifestations including diabetes mellitus.
- Current smoker or one that has stopped smoking less than 2 years prior to enrollment (self-report).
- Gross oral pathology other than the periodontal disease.

- Treatment with antibiotics for any medical or dental condition within 1 month prior to the screening examination.
- Chronic treatment (i.e., two weeks or more) with any medication known to affect periodontal status (e.g., phenytoin, calcium antagonists, cyclosporin, coumadin, non-steroidal anti-inflammatory drugs, aspirin) within one month of the screening examination.
- Ongoing medications initiated less than three months prior to enrollment (i.e., medications for chronic medical conditions must be initiated at least three months prior to enrollment).
- Significant organ disease including impaired renal function, heart murmur, history of rheumatic fever or valvular disease, or any bleeding disorder.
- Individuals with prosthetic material used for intra-cardiac repair (e.g. for congenital heart disease), or intra-cardiac devices, cardiac transplant, infective endocarditis and individuals who have had previous infectious complications of prosthetic joint infections
- Infectious diseases such as hepatitis, HIV or tuberculosis.
- Anemia or other blood dyscrasias.
- Anticoagulant therapy or drugs, such as heparin or warfarin.
- Severe unrestored caries, or any condition that is likely to require antibiotic treatment over the trial.
- Pregnant, or expect to become pregnant within the next several months.
- Females of child-bearing capacity not using any form of contraceptive methods
- Anything that would place the individual at increased risk or preclude the individual's full compliance with or completion of the study.

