6.2 Visit 2: Baseline

(Day 0 +/- 5 days)

- Study personnel will update medical history, including concomitant medication, enquire about potential adverse events related to the dental exam performed during screening and ask continuance criteria questions.
- Study personnel will record the subject's vital signs (blood pressure and pulse).
- A dental examiner will verify the previously performed intraoral exam and assess for potential adverse events.
- Dental examiner will perform a comprehensive periodontal screening examination that includes Plaque Index (PI), Gingival Index (GI), Pocket Depth (PD), Bleeding on Probing (BOP) and Clinical Attachment Levels (CAL).
- The dental examiner will collect two separate subgingival plaque samples from the interdental sulcus of the teeth that are selected for a gingival biopsy (see appendix II). Dental implant sites will not be considered for subgingival plaque samples.
- A small gingival tissue biopsy sample will be removed from underneath the papillae, buccally and lingually, to include the col area of depth of the osseous crest. Biopsies will be collected by a study dentist and performed under local anesthesia. Absorbable sutures will be used to close the interproximal papillae.
- The dental examiner will deliver 1 customized acrylic stent that will be used in a different sextant from the one that the biopsy was performed. The sextant selected will be the right posterior sextant (maxillary or mandibular), except when fewer than two teeth are present and adjacent without significant diastema.
- The participant will be instructed to defer oral hygiene measures in the experimental sextant, to wear the customized stents during brushing and to discontinue flossing throughout his/her mouth. The participant will continue to use his/her standard toothpaste and toothbrush. Participants will be informed to avoid crunchy or sticky food (e.g. apples and carrots), and use of mouthwashes during baseline through visit 5 (Day 21).
- Subjects will be monitored for safety every week during the induction of experimental biofilm overgrowth through 21 days. Any site undergoing CAL

increase of >2 mm from the baseline measurement will be deemed as “progressing.” That site will not be included in data analysis, and will receive scaling and root planing treatment as a rescue therapy.

- Subjects will be given parking vouchers for the UNC Dogwood parking deck and scheduled to return for visit 3.

6.3 Visit 3

(Day 7 +/- 5 days)

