Visit 3 may occur within 7 days of visit 2 (+/-5 days). The following procedures will be performed:

- Study personnel will update medical history, including concomitant medication, enquire about potential adverse events related to the dental procedures and ask continuance criteria questions.
- Study personnel will record the subject’s vital signs (blood pressure and pulse).
- A dental examiner will verify the previously performed intraoral exam and assess for potential adverse events.
- Dental examiner will perform a comprehensive periodontal screening examination that includes Plaque Index (PI), Gingival Index (GI), Pocket Depth (PD), Bleeding on Probing (BOP) and Clinical Attachment Levels (CAL).
- A follow-up for verifying the healing of the gingival biopsy will be completed.
- The participant will be re-instructed to defer oral hygiene measures in the selected sextant and to continue wearing the customized stents during brushing of the non-selected sextants.
- Adverse events will be monitored and recorded as necessary.
- The subject will be given a parking voucher for the Dogwood deck, and Visit 4 will be scheduled.

6.4 Visit 4

(Day 14 +/- 5 days)

Visit 4 may occur within 7 days +/-5 days of day 7. The following procedures will be performed:

- Study personnel will update medical history, including concomitant medication, enquire about potential adverse events related to the dental procedures and ask continuance criteria questions.
- Study personnel will record the subject’s vital signs (blood pressure and pulse).

- A dental examiner will verify the previously performed intraoral exam and assess for potential adverse events.
- Dental examiner will perform a comprehensive periodontal screening examination that includes Plaque Index (PI), Gingival Index (GI), Pocket Depth (PD), Bleeding on Probing (BOP) and Clinical Attachment Levels (CAL).
- The participant will be re-instructed to defer oral hygiene measures in the selected sextant and to continue wearing the customized stents during brushing of the non-selected sextants.
- Adverse events will be monitored and recorded as necessary.
- The subject will receive a parking voucher to the Dogwood parking deck, and Visit 5 will be scheduled.

6.5 Visit 5

(Day 21 +/- 5 days)

Visit 5 may occur within 7 days +/-5 days of day 14. The following procedures will be performed:

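### Analgesic advice after the visit 2 biopsy, given as the 21-day SIBO challenge starts, does not steer participants away from NSAIDs or aspirin: a minor point, bearing mainly on some visit 3 clinical measurements

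*Combined protocol and SAP*

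**What the plan says.** - **Advice (section 2.3.1).** "Subjects receiving biopsy and/or scaling and root planing procedures will be encouraged to use over the counter analgesics". The only qualifier is the participant's medication tolerance; no drug class, dose or duration is given.
- **Timing (section 6.2).** The first gingival biopsy is at visit 2. At the same visit, "The dental examiner will deliver 1 customized acrylic stent", for use in a different sextant, and the participant stops cleaning that sextant.
- **NSAIDs in the rationale (section 2.2).** Anti-inflammatory agents, with NSAIDs named, "have been used to prevent and slow the progression of experimental and human periodontitis".
- **The only NSAID or aspirin rule (section 5.2).** The exclusion covers "Chronic treatment (i.e., two weeks or more) with any medication known to affect periodontal status", with a list of examples that ends "non-steroidal anti-inflammatory drugs, aspirin) within one month of the screening examination". It looks back from screening and does not reach short use during the study.
- **Other conduct rules.** Section 6.2 asks participants to avoid certain foods and mouthwashes up to visit 5. Section 7.3.1 lists ice and avoidance of hot drinks after the biopsy, as examples. Neither mentions the choice of analgesic.
- **Medication record (sections 6.2 to 6.5).** "Study personnel will update medical history, including concomitant medication" appears at visit 2 and again at visits 3, 4 and 5. Section 11.3 makes no use of it.

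**The concern.** The study provokes gingival inflammation in order to measure it. On the day the provocation starts, participants are encouraged to take a type of product that includes drugs the protocol itself treats as disease-modifying. The investigators already control smaller influences, such as food and mouthwash, over the same 21 days. If some participants took an NSAID or aspirin and it reduced the early response, the visit 3 scores for gingival index and bleeding on probing could be lowered. Probing depth and attachment level might move slightly too, since section 7.1 says probe penetration varies with the degree of inflammation. These values enter the section 11.3 models of change over visits 2, 3, 4 and 5.

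**Working it through.** The plan states no figure on this point, so there is none to reproduce. The documents fix only the timing.

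**Inputs from the documents.** Visit 3 is 7 days after visit 2, plus or minus 5 (section 6.3). Visit 4 is day 14 plus or minus 5, and visit 5 is day 21 plus or minus 5 (sections 6.4 and 6.5). Visit 2 is day 0 plus or minus 5 (section 6.2). Enrollment is 72.

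**Inputs assumed.** A 3-day or 7-day course, 20% to 50% of participants taking an NSAID or aspirin, and visit 3 dates spread evenly over the window.

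**Step 1: visit windows, in days after the biopsy.** With visit 2 on day 0:
- visit 3: 7 - 5 = 2 to 7 + 5 = 12, which is 11 permitted days;
- earliest visit 4: 14 - 5 = 9;
- earliest visit 5: 21 - 5 = 16.

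On the widest reading, with visit 2 on day +5, the earliest visit 4 is 9 - 5 = 4 days after the biopsy and the earliest visit 5 is 16 - 5 = 11 days after it.

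**Step 2: overlap of use with the visits.** The count depends on whether the biopsy day is the first day of the course, so both conventions are shown.

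| Assumed use | Last day of use | Visit 3 days overlapped | Days to earliest visit 5 (visit 2 on day 0) | Days to earliest visit 5 (widest reading) |
|---|---|---|---|---|
| 3 days, biopsy day included | 2 | 1/11 = 9.1% | 16 - 2 = 14 | 11 - 2 = 9 |
| 3 days after the biopsy day | 3 | 2/11 = 18.2% | 16 - 3 = 13 | 11 - 3 = 8 |
| 7 days, biopsy day included | 6 | 5/11 = 45.5% | 16 - 6 = 10 | 11 - 6 = 5 |
| 7 days after the biopsy day | 7 | 6/11 = 54.5% | 16 - 7 = 9 | 11 - 7 = 4 |

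With visit 2 on day 0, visit 4 is reached only by use lasting to day 9 or later. On the widest reading a 7-day course could touch the earliest visit 4 dates.

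**Step 3: share of visit 3 records taken during use.** Share = proportion using x proportion of the window overlapped.
- Low: 0.20 x 1/11 = 1.8%, or 0.018 x 72 = about 1 record.
- High, biopsy day included: 0.50 x 5/11 = 22.7%, or about 16 records.
- High, biopsy day not included: 0.50 x 6/11 = 27.3%, or about 20 records.

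If visits cluster on the nominal day 7, only use that lasts to day 7 overlaps them.

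**Step 4: which analyses are reached.** Visit 2 tissue is taken before any post-biopsy drug. The primary expression tests in section 11.3 compare visit 2 with visit 5 and do not use visit 3. None of the courses above reaches visit 5. Analgesics taken after the visit 5 biopsy follow the last analyzed sample. That leaves the clinical mixed models, mainly at one of their four visits. No step yields an effect size, because the documents say nothing about how far a short course changes a clinical score.

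**The case against.** The strongest reply is that the mechanism is assumed. Section 2.2 speaks of NSAIDs as a treatment for periodontitis, whereas section 4 calls SIBO an experimental gingivitis model. The only duration that the protocol links to periodontal status is two weeks or more. Nothing says that a few days of an over-the-counter product lowers gingival index or bleeding. The section 2.3.1 wording also covers acetaminophen, so NSAID use is itself an assumption. Named-drug advice may sit in the Manual of Procedures or SOPs that the protocol mentions, and the section 7.3.1 list is not exhaustive. Continuance questions at each visit, with loss of eligibility as a possible reason for discontinuation (section 5.4.1), give some handle on prolonged use.

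Most of this stands, and it is why the point is minor. It does not alter what the protocol text tells participants: analgesics are encouraged, and no class is preferred or discouraged. Continuance questions and unseen manuals do not change that instruction.

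A reader might infer more, in three ways that the documents do not support:
- **That the primary AIM2/IFI16 result is compromised.** The timing above speaks against this for short courses; only use near visit 5 would matter.
- **That the group comparison is biased.** Nothing indicates that use would differ between healthy participants and those with severe periodontitis.
- **That records or participants with NSAID use should be left out of a sensitivity analysis.** This would select on a post-baseline variable that may itself track pain or inflammation, and it is out of proportion to an effect that has not been shown.

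Section 3.2 does list clinical measurements among the primary outcomes. However, section 11.3 ties them to secondary hypotheses, and section 11.1 states no hypothesis about them.

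**Conclusion.** The point holds as a minor, inexpensive improvement. The protocol encourages analgesics at the start of an induced-inflammation challenge and leaves open a class that its own rationale regards as active against periodontitis. The plausible reach is some visit 3 clinical values: roughly 1 to 20 of 72 records taken during use, given 20% to 50% users, courses of 3 or 7 days and evenly spread visits. All of these are assumptions. Whether those values would change, and by how much, cannot be determined from the documents.

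**What to change.** 1. In sections 2.3.1 and 6.2 and in the section 7.3.1 post-operative instructions, name a non-NSAID analgesic (for example acetaminophen), subject to tolerance, as first choice after the visit 2 biopsy.
2. Beside the food and mouthwash advice in section 6.2, ask participants to avoid NSAIDs and aspirin until the visit 5 biopsy unless clinically needed. This also covers use near visit 5, the one route to the primary tissue contrast.
3. Tabulate NSAID and aspirin use by group, with agent and dates where recorded, from the concomitant medication already updated at visits 3 to 5.

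The planned analyses stay as they are, with no added exclusions. The cost is a few sentences and one table. The downside is slightly less analgesic choice for participants; pain relief remains available, and clinical need overrides the request.
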